#### 4.2.2 Secondary Endpoints

1. Change in RBC transfusion requirements.
2. The proportion of patients who achieve granulocyte or platelet hematologic improvement as defined by the modified IWG response criteria(39).
3. Change in serum ferritin levels from baseline to the end of the study as measured on a monthly basis.
4. Safety and tolerability profile as measured by grade 3 and 4 non-hematologic adverse events

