### 7.6.3 Renal Impairment

Serum creatinine and proteinuria should be monitored during the study as stated in Table 2.

Deferasirox can cause acute renal failure, fatal in some patients and requiring dialysis in others. Postmarketing experience showed that most fatalities occurred in patients with multiple comorbidities and who were in advanced stages of their hematological disorders. In the clinical trials, deferasirox-treated patients experienced dose-dependent increases in serum creatinine.

Measure serum creatinine and determine the glomerular filtration rate (GFR, estimated by the MDRD method) before initiating therapy in all patients.

Deferasirox is contraindicated in patients with an estimated GFR less than 40 mL/minute or serum creatinine greater than 2 times the age-appropriate upper-limit-of-normal (ULN). Renal tubular damage, including Fanconi's Syndrome, has been reported in patients treated with deferasirox, most commonly in children and adolescents with beta-thalassemia and serum ferritin levels <1500 mcg/L.

Deferasirox will be administered and dosed at the discretion of the treating clinician based on renal function as measured by serum creatinine and via the estimated GFR.

Intermittent proteinuria of unclear significance was also noted in clinical trials with deferasirox. The level of proteinuria will be measured per Table 2 (at baseline before treatment, at 6 months and again at 12 months) strictly for monitoring. Deferasirox will be administered and dosed at the discretion of the treating clinician based on the

results of monitoring for proteinuria. However, given the intermittent nature of proteinuria experienced with deferasirox and its unclear significance, there is no contraindication to the administration of deferasirox based on level of proteinuria.

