#### **7.6.6 Hepatic Impairment**

Liver function tests should be monitored during the duration of the trial as indicated in **Table 2**.

Deferasirox can cause hepatic injury, fatal in some patients. Hepatic toxicity appears to be more common in patients greater than 55 years of age. Hepatic failure was more common in patients with significant comorbidities, including liver cirrhosis and multiorgan failure.

Consider dose modifications or interruption of treatment for severe or persistent elevations.

Patients with mild (Child-Pugh A) or moderate (Child-Pugh B) hepatic impairment may be at higher risk for hepatic toxicity. In a single dose (20 mg/kg) study in patients with varying degrees of hepatic impairment, deferasirox exposure was increased compared to patients with normal hepatic function. The average total (free and bound) AUC of deferasirox increased 16% in 6 patients with mild (Child-Pugh A) hepatic impairment, and 76% in 6 patients with moderate (Child-Pugh B) hepatic impairment compared to 6 patients with normal hepatic function. The impact of severe (Child-Pugh C) hepatic impairment was assessed in only 1 patient.

Avoid the use of deferasirox in patients with severe (Child-Pugh C) hepatic impairment. For patients with moderate (Child-Pugh B) hepatic impairment, the starting dose should be reduced by 50%. Closely monitor patients with mild (Child-Pugh A) or moderate (Child-Pugh B) hepatic impairment for efficacy and adverse reactions that may require dose titration.

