### 7.6.10 Gastrointestinal Ulceration, Hemorrhage, and Perforation

GI hemorrhage, including deaths, has been reported, especially in elderly patients who had advanced hematologic malignancies and/or low platelet counts. Nonfatal upper GI irritation, ulceration and hemorrhage have been reported in patients, including children and adolescents, receiving deferasirox. Monitor for signs and symptoms of GI ulceration and hemorrhage during deferasirox therapy and promptly initiate additional evaluation and treatment if a serious GI adverse event is suspected. The risk of gastrointestinal hemorrhage may be increased when administering deferasirox in combination with drugs that have ulcerogenic or hemorrhagic potential, such as nonsteroidal anti-inflammatory drugs (NSAIDs), corticosteroids, oral bisphosphonates, or anticoagulants. There have been reports of ulcers complicated with gastrointestinal perforation (including fatal outcome).

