#### Definitions:

**Adverse Event (AE)** - Any untoward medical occurrence in a patient or clinical investigation subject administered a pharmaceutical product, medical treatment or procedure and which does not necessarily have to have a causal relationship with this treatment. An adverse event can therefore be any unfavorable and unintended sign (including

an abnormal laboratory finding, for example), symptom, or disease temporally associated with the use of a medicinal product, medical treatment or procedure whether or not considered related to the medicinal product.

**Life-threatening AE** – Any adverse event that places the patient or subject, in view of the investigator, at immediate risk of death from the reaction.

**Unexpected AE** – An adverse event is “unexpected” when its nature (specificity), severity, or frequency are not consistent with (a) the known or foreseeable risk of adverse events associated with the research procedures described in the Protocol-related documents, such as the IRB-approved research protocol, informed consent document and other relevant sources of information such as product labeling and package inserts; and are also not consistent with (b) the characteristics of the subject population being studied including the expected natural progression of any underlying disease, disorder or condition any predisposing risk factor profile for the adverse event.

**Attribution** - The following are definitions for determining whether an adverse event is related to a medical product, treatment or procedure:

- An adverse event is “**related or possibly related to the research procedures**” if in the opinion of the PI, it was more likely than not caused by the research procedures.
- Adverse events that are solely caused by an underlying disease, disorder or condition of the subject or by other circumstances unrelated to either the research or any underlying disease, disorder or condition of the subject are not “related or possibly related.”
- If there is any question whether or not an adverse event is related or possibly related, the adverse event should be reported.

The Cancer Consortium Expedited Reporting Form should be completed for all adverse events that meet the expedited reporting requirements. The AE form (see **Appendix I**) should be faxed to the FHCRC Research Coordinator at [contact] within 10 business days of study staff awareness. All available information should be submitted.

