### **8.2 Study-Specific AE Capture**

Please refer to the package insert of deferasirox for a listing of specific expected AEs.

AEs will be reviewed and captured in the source documentation. AEs occurring from enrollment through 30 days after the last administration of the study treatment will be captured in protocol-specific case report forms (**Appendix J**).

The following events are not recorded as AEs in this study:

- Disease progression or relapse.
- Planned medical or surgical procedures in and of themselves, including those that require hospitalization (e.g., surgery, endoscopy, biopsy procedures) are not considered AEs.
- Abnormal laboratory values grade < 3 (CTCAE v4.03).

In accordance with institutional policy, all SAEs which in the opinion of the PI or designee meet all three of the following criteria will be reported to the IRB within 10 calendar days of learning of the problem:

1. unexpected
2. related or possibly related to the research
3. serious or suggests that the research places research participants or others at greater risk of physical or psychological harm than was previously known or recognized

All other SAEs and deaths, not meeting the expedited reporting criteria, will be reported to the IRB as part of the annual continuation review report to the IRB.

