### 9.4.1 AE Grading

Toxicities will be graded using the NCI Common Terminology Criteria for Adverse Events (CTCAE) Version 4.03. Citing the website under this section in the protocol rather than printing the entire document is sufficient unless the study is modifying the criteria. The scale in its entirety can be found at:

[http://evs.nci.nih.gov/ftp1/CTCAE/CTCAE\\_4.03\\_2010-06-14\\_QuickReference\\_8.5x11.pdf](http://evs.nci.nih.gov/ftp1/CTCAE/CTCAE_4.03_2010-06-14_QuickReference_8.5x11.pdf)

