### **12.3 Other Parameters**

The secondary endpoints change in RBC transfusion requirements, change in serum ferritin, and safety and tolerability will be assessed in a continuous fashion during the entire duration of the study. Patients will remain on study for a maximum of one year. Patients will be assessed for AE and SAEs while they remain enrolled into the study. Patients will have an end of study visit day 30 following completion or withdrawal from the study.

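### Secondary endpoint 4 counts only grades 3 and 4, so a fatal (grade 5) non-hematologic event falls outside the trial's stated safety endpoint

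*Combined protocol and SAP*

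**What the plan says.** Section 4.2.2, item 4, sets the safety endpoint: "Safety and tolerability profile as measured by grade 3 and 4 non-hematologic adverse events". The grading rule is in Section 9.4.1: "Toxicities will be graded using the NCI Common Terminology Criteria for Adverse Events (CTCAE) Version 4.03". That section gives a link to the scale and states no modification of it.

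The other places that mention this endpoint do not change the grade range. Section 3.2 names safety and tolerability without grades. Section 12.3 gives the timing and adds: "Patients will be assessed for AE and SAEs while they remain enrolled into the study". Section 15.0 promises descriptive statistics and has no text on safety analysis.

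The protocol foresees fatal non-hematologic toxicity in three organ systems:

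- Renal (Section 7.6.3): "Deferasirox can cause acute renal failure, fatal in some patients and requiring dialysis in others".
- Hepatic (Section 7.6.6): "Deferasirox can cause hepatic injury, fatal in some patients".
- Gastrointestinal (Section 7.6.10): "GI hemorrhage, including deaths, has been reported".

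The definitions in Section 8.1 say that an adverse event "does not necessarily have to have a causal relationship with this treatment", so endpoint 4 does not depend on attribution to the drug.

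**The concern.** A safety endpoint normally takes in everything at or above a severity threshold. This one names two grades and stops below the worst outcome. A summary built on its wording would count a patient with a grade 4 hepatic event and leave out a patient whose only qualifying event was fatal. If events were summarised by worst grade, a patient who passed through grade 4 and then died of the same event would also leave the count, so that a worse outcome would improve the reported figure.

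What is at stake is how the trial's safety result reads. The trial is single-arm with 25 patients and, by Section 16.0, has no stopping rule for excessive toxicity. The descriptive summary is therefore how readers will judge tolerability.

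**Working it through.** The plan gives no figure for endpoint 4, so there is none to reproduce. The check has two parts.

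**1. Does any passage bring fatal events into the endpoint?**

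- Section 4.2.2 names grades 3 and 4, not a threshold of grade 3 or higher.
- Section 9.4.1 adopts CTCAE v4.03 unmodified. Death as grade 5 is a property of that scale and is not spelled out in the protocol.
- Sections 3.2, 12.3 and 15.0 add no grade range. Section 12.3 adds assessment of AEs and SAEs, which concerns collection and not the content of endpoint 4.
- Section 8.2 puts AEs on case report forms. It leaves out laboratory abnormalities below grade 3 but sets no upper grade limit, so fatal AEs are collected.
- Section 9.1 makes fatal events SAEs, and Section 9.2 requires them to be reported within 24 hours. For the IRB, Section 8.2 adds: "All other SAEs and deaths, not meeting the expedited reporting criteria, will be reported to the IRB", as part of the annual review. Sections 10.0 and 16.0 provide for DSMB review of toxicity every six months.

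The data are therefore available and reviewed, but no passage places a grade 5 event inside endpoint 4.

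**2. How large is the effect of one omitted event?**

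Inputs: n = 25 (Section 15.0). Assumptions: the endpoint is reported as patients with at least one qualifying event out of 25, and the patient who dies has no other qualifying event.

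Shift = 1/25 = 4 percentage points, whatever the other counts.

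Exact (Clopper-Pearson) 95% intervals:

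| Fatal event counted | Fatal event omitted |
|---|---|
| 1/25 = 4% (0.1 to 20.4%) | 0/25 = 0% (0 to 13.7%) |
| 6/25 = 24% (9.4 to 45.1%) | 5/25 = 20% (6.8 to 40.7%) |

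For 0/25 the upper limit is 1 − 0.025^(1/25) = 0.137. For 1/25 the lower limit is 1 − 0.975^(1/25) = 0.001.

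**How likely is such an event?** The documents do not say. With an assumed per-patient probability p of a fatal non-hematologic AE, the chance of at least one in 25 patients is 1 − (1 − p)^25:

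- p = 1%: 0.22
- p = 2%: 0.40
- p = 4%: 0.64

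These values show a range and are not a projection.

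Sample size, type I error and power rest on erythroid response and are unaffected.

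**The case against.** The strongest reply is that deaths are already well covered. They are recorded on case report forms, are SAEs by definition, reach the IRB, and are seen by a DSMB that can end the study. Nothing in the plan says they will be left out of the results. This stands, and it limits the point to the wording of the endpoint. A reader might infer that deaths would surface only in SAE and IRB reports, or would go unreported. The documents do not support that, because Sections 8.2, 10.0 and 16.0 also route them through case report forms and the DSMB.

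A second reply is that the two grades are shorthand for severe toxicity. That may be what was meant, but Section 15.0 has no safety text that would settle it, and the literal reading excludes deaths.

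A third is that the key premise, death as grade 5, lies outside the text. The protocol adopts the scale by citation, so the premise is stated here as an assumption.

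A fourth is that the 4-point shift belongs to an analysis the plan does not specify. This is correct, and the figure is conditional for that reason.

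A reader might also take the 8% first-year deaths in Section 2.4 (25 × 0.08 = 2 patients) as the number the endpoint would miss. That is not supported. The figure is not limited to fatal non-hematologic AEs, and Section 8.2 does not record disease progression as an AE. The 28 and 26 deaths in the two earlier MDS trials in Section 2.2 were all judged unrelated to the drug. They do not size the problem either, since endpoint 4 does not depend on attribution.

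Finally, a reader might infer that endpoint 4 is also wrong because it has no measure of discontinuation. Sections 2.2 and 2.4 describe earlier experience in those terms, but the plan does not undertake to report it. A table of discontinuations by reason would be an optional addition. In such a table, non-response at 6 months should not be treated as a mandatory exit: Sections 7.3 and 7.4 only offer non-responders alternatives, and therapy may run to one year.

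**Conclusion.** The point holds as a defect in the definition of one descriptive secondary endpoint. As worded, endpoint 4 counts a non-hematologic event at grade 4 and omits it when fatal, although the protocol itself describes fatal renal, hepatic and gastrointestinal events. No test, stopping rule or design figure depends on it, and data capture and safety oversight are not at fault.

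The size is 4 percentage points per omitted patient. This rests on two assumptions: per-patient reporting in 25 patients, and no other qualifying event in that patient. The conclusion also takes death as grade 5 of the cited scale. The expected number of such patients is unknown. The change should be made because the stated rule gives a wrong count and correcting it is easy.

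**What to change.** Reword item 4 of Section 4.2.2 so that safety and tolerability are measured by non-hematologic adverse events of grade 3 or higher (grades 3-5), and state that fatal events will also be listed separately.

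The cost is a wording change and one listing, from data that Sections 8.2, 9.1 and 9.2 already require. The reported figure may be slightly less favourable. Deaths from disease progression alone would stay outside the endpoint, because Section 8.2 does not record progression as an AE. Sample size and the response analysis do not change.

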### **2.3 Study Agent**

Patients will receive oral deferasirox which has been approved by the FDA for the treatment of chronic iron overload due to blood transfusions in patients 2 years of age or older. Deferasirox will be administered to achieve a ferritin < 100 ng/mL and, since it is approved for chelation and used regularly for this purpose as a standard of care, the dosing and schedule will be at the discretion of the treating clinician based on overall iron loading (ferritin), renal function, hepatic function, blood counts, and clinical condition / performance status. Contraindications include the following: Serum creatinine greater than two-times the upper limit of normal (ULN) or glomerular filtration rate (GFR) of less than 40 mL/min, poor performance status, high risk MDS, advanced malignancies, platelet count of less than 50,000, pregnancy, and/or known hypersensitivity to deferasirox.

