### 4.2 Endpoints

#### 4.2.1 Primary Endpoint

The primary endpoint is the proportion of patients that achieve erythroid hematologic improvement as defined by the modified IWG response criteria at 6 months(39).

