#### **7.6.9 Cytopenias**

There have been post-marketing reports (both spontaneous and from clinical trials) of cytopenias in patients treated with deferasirox. Most of these patients had pre-existing hematological disorders that are frequently associated with bone marrow failure. The relationship of these episodes to treatment with deferasirox is uncertain. In line with the standard clinical management of such hematological disorders, complete blood counts will be monitored regularly. Given the nature of this particular clinical trial in the setting of MDS patients, dose interruptions or modifications in patients who develop cytopenias or have worsening of cytopenias are at the discretion of the treating clinician.

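### Platelet and neutrophil falls enter no prespecified endpoint, although rises in the same counts are reported as improvement

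*Combined protocol and SAP*

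**What the plan says.** Section 4.2.2 lists four secondary endpoints. Item 4 is "Safety and tolerability profile as measured by grade 3 and 4 non-hematologic adverse events". Item 2 is "The proportion of patients who achieve granulocyte or platelet hematologic improvement", judged by the modified IWG criteria in Appendix G. Item 1 is "Change in RBC transfusion requirements" and item 3 is the change in serum ferritin. The primary endpoint (4.2.1) is erythroid improvement at 6 months.

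Section 7.6.9 states: "There have been post-marketing reports (both spontaneous and from clinical trials) of cytopenias in patients treated with deferasirox". It adds that most of those patients already had blood disorders and that the link to the drug is uncertain. Section 2.3 includes among its contraindications "platelet count of less than 50,000, pregnancy, and/or known hypersensitivity to deferasirox", and section 5.2 excludes patients with platelets at or below 50,000. Section 7.6.10 states: "GI hemorrhage, including deaths, has been reported, especially in elderly patients who had advanced hematologic malignancies and/or low platelet counts".

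The objectives (3.2) and section 12.3 mention safety and tolerability without the non-hematologic limit, but give no other way of measuring them.

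**The concern.** The trial's hypothesis is that chelation changes blood counts. Section 2.2 offers selective toxicity to MDS progenitors as one possible mechanism and acknowledges that clinical data are sparse in minimally transfused patients and below a ferritin of 1,000 ng/mL. An effect on the marrow in either direction is thus an open question in this population. Yet the endpoints report platelets and neutrophils in one direction only.

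With no control arm, a reader cannot judge a number of improvements in counts that also vary with the disease unless the number of deteriorations stands beside it. What is at stake is the trial's secondary conclusion on hematologic benefit and risk. The primary test is not affected.

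**Working it through.** No figure in the plan belongs to this point. The check is therefore a comparison of definitions, followed by arithmetic on size.

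**Step 1. Can a platelet or neutrophil fall change any listed endpoint?**

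- Primary (4.2.1): erythroid improvement only. No.
- Secondary 1: red-cell transfusion need can move either way, so worsening anemia can show here indirectly. Platelets and neutrophils cannot.
- Secondary 2: Appendix G counts increases only. For platelets starting above 20 x 10^9/L it asks for a rise of at least 30 x 10^9/L. For neutrophils it asks for at least a doubling and an absolute rise above 0.5 x 10^9/L. A fall scores the same as no change.
- Secondary 3: ferritin. No.
- Secondary 4: non-hematologic events only, so the fall itself is outside it at any grade. A resulting bleed or infection can be counted.

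Take an illustrative patient who starts at 80 x 10^9/L platelets and falls to 30. That patient is a non-responder in endpoint 2 and, for the fall itself, absent from endpoint 4.

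**Step 2. Does the Appendix G loss rule fill the gap?** It describes a decrement of at least 50% in granulocytes or platelets, but measures it from the maximum response level, under progression or relapse after improvement. It cannot apply to a patient who never responded, and it is not listed as an endpoint.

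**Step 3. What is collected outside the endpoints?**

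- Blood counts at baseline and monthly (Table 2, 12.2), and platelet transfusions at each visit (7.3).
- Adverse events on case report forms. Laboratory values below grade 3 and disease progression are left out, but hematologic events as such are not (8.2).
- Serious events regardless of causality (9.2).
- Semi-annual DSMB review of response and toxicity (10.0, 16.0).

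The data exist. What is missing is a commitment to report the falls beside the gains.

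**Step 4. Size of the side that is reported.** Inputs: platelet and neutrophil response rates of 13% and 22% from the post-hoc analysis cited in section 2.2, and N = 25 from section 15.0.

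- All 25 evaluable (the maximum): 0.13 x 25 = 3.25 and 0.22 x 25 = 5.5 patients.
- Appendix G requires pretreatment platelets below 100 x 10^9/L or neutrophils below 1.0 x 10^9/L, while entry requires only anemia. If 10 patients qualified for each (assumption): 1.3 and 2.2.
- If a quarter qualified (assumption, 6.25 patients): about 0.8 and 1.4.

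**Step 5. What 25 patients could show about falls.** The documents give no rate, so a range is assumed. The chance of at least one event is 1 - (1 - p)^25.

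- p = 5%: 0.723
- p = 10%: 0.928
- p = 20%: 0.996

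Exact two-sided 95% intervals:

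- 0/25: 0 to 13.7%
- 3/25: 2.5% to 31.2%
- 5/25: 6.8% to 40.7%

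A table would probably show events if they are not rare, but would estimate their rate imprecisely.

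**The case against.** The strongest reply is that nothing is hidden. Counts are taken monthly, grade 3 or higher laboratory events are captured, and the DSMB sees toxicity with no non-hematologic limit. This stands. A reader might infer that cytopenias go unwatched, and the documents do not support that. What remains is that neither event capture nor DSMB review commits the trial to publish falls beside gains, and a large fall that stays below grade 3 leaves no adverse event record.

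A reader might also infer that no cytopenia of any kind can reach an endpoint. That goes too far: worsening anemia can raise transfusion need, and the hemorrhage described in 7.6.10 is a bleeding event that endpoint 4 can count.

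Nor do the documents establish cytopenia as an effect of deferasirox. Section 7.6.9 calls the relationship uncertain, and 7.6.10 does not say that the drug lowered the platelets. Section 2.4 lists mainly gastrointestinal, skin and renal reactions, with raised creatinine in 37% of MDS patients, so a focus on non-hematologic events has a rationale. It does not explain why the same counts are scored when they rise.

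It would be tempting to say that falls may be as common as rises, so that the net effect is nil. The documents give no rate of falls, so this has no support. Appendix G also requires responses to last at least 8 weeks and pretreatment counts to average at least two measurements. Section 12.2 takes the most recent screening labs as baseline, which weakens the second safeguard but not the first. Brief fluctuation is therefore not simply scored as benefit.

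Finally, a single arm in a disease that itself causes cytopenias cannot attribute falls to the drug. That is correct, and it is why the addition should be descriptive and adjusted for baseline.

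**Conclusion.** The point holds as a gap in prespecified reporting. Platelet and neutrophil rises are a secondary endpoint, while falls in the same counts belong to none. Surveillance is in place, and the primary decision rule of 4 or more responses in 25 is untouched.

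The improvements reported without a counterpart number at most 3.25 and 5.5 patients. This assumes that the cited cohort's rates carry over and that all 25 patients are evaluable; under the Appendix G thresholds the numbers are likely to be lower. Carry-over is itself doubtful, because that cohort was transfusion-dependent according to its cited title, whereas this trial admits patients from a ferritin of 100 ng/mL. The number of falls to expect cannot be derived from the documents. The change is cheap and should be made, because it affects what the trial can say about hematologic safety.

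**What to change.** Amend endpoint 4 in section 4.2.2 so that it also reports, descriptively:

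- the number of patients with grade 3-4 (CTCAE v4.03) thrombocytopenia or neutropenia that is worse than their baseline grade, with no minimum duration;
- the shift from pretreatment in platelets and ANC, from the monthly blood counts, using the same pretreatment value as endpoint 2.

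Show both beside endpoint 2 among the same patients, and state that a single arm cannot separate drug effect from MDS.

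Two alternatives are less suitable. Applying the Appendix G 8-week durability rule to falls would miss acute or reversible harm. A bare count of patients below 50 x 10^9/L would flag a trivial drop such as 52 to 49.

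The cost is one amended endpoint and one table. No new tests are needed, and N, alpha and power do not change. The downside is that some falls will reflect MDS itself and must be reported as such.
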